2.4.2 Concomitant therapies

Concomitant therapies are defined as any medications (excluding study treatment and antineoplastic treatments) and significant non-drug therapies (including physical therapy and blood transfusions) administered in the study and are recorded in the Concomitant Medications/significant non-drug therapies eCRF. These therapies will be coded using the WHO Drug Reference Listing (WHO DRL) dictionary that employs the WHO Anatomical Therapeutic Chemical (WHO ATC) classification system.

Any concomitant therapies starting prior to or after the start of study treatment will be listed.

Concomitant and significant non-drug therapies will be summarized by ATC class and preferred term to include medications or therapies starting on or after the start of study treatment but starting no later than 30 days after last dose of study treatment.

All medications or therapies starting prior to the first dose of study treatment and continuing after the start of study treatment will be listed.

The imputation of a concomitant medication start date will follow the same conventions as for an AE start date (see [Section 5.1.2](#)). No imputation will be performed for concomitant medication end dates.

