6.4.1 Permitted concomitant therapy requiring caution and/or action

Therapeutic treatment with hematopoietic colony-stimulating growth factors G-CSF or GM-CSF may only be initiated after the first two cycles in the dose escalation part of the study, unless the patient has already experienced a DLT. If available GM-CSF is preferred over G-CSF (Eyles 2006).

Treatment with erythroid stimulating agents may not be initiated during the first two cycles in the dose escalation part of the study, unless the patient has already experienced a DLT. If a patient is using an erythroid stimulating agents prior to enrollment (at least 2 weeks before start of study treatment), they may continue at the same dose.

Anticoagulants are permitted if the patient is already at stable doses of warfarin or taking stable doses of low molecular weight heparin for >2 weeks at time of first dose and INR should be monitored as clinically indicated per investigator's discretion. However, ongoing anticoagulant therapy should be temporarily discontinued to allow tumor biopsy according to the institutional guidelines.

Anti-hypertensives are allowed as concomitant medications; however, because transient hypotension has occurred during infusions of monoclonal antibodies, consideration should be given to withholding anti-hypertensive medications for 12 hours prior to infusion with MCS110 and PDR001.

Statins should be used with caution since CK elevations are commonly seen and transient CK elevations were noted in healthy volunteers and patients studies with MCS110.

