10.3 Treatments (study treatment, concomitant therapies, compliance)

For each of MCS110 and PDR001, the actual dose and duration in days of treatment as well as the dose intensity (actual dose received/actual duration) and relative dose intensity (the ratio of dose intensity to planned dose/planned duration) will be listed and summarized by means of descriptive statistics by treatment group. Categories for relative dose intensity of MCS110 or PDR001 will be specified as < 0.5 , $\geq 0.5 - < 0.75$, $\geq 0.75 - < 0.9$, $\geq 0.9 - < 1.1$ and ≥ 1.1 . The number and proportion of patients within each category will be presented by treatment group.

Concomitant medications and significant non-drug therapies prior to and after the start of the study treatment will be listed by patient and summarized by ATC term and treatment group.

The reason for discontinuation from treatment will be summarized and listed, along with dates of first and last dose of MCS110 and PDR001 (if applicable), duration of exposure to MCS110 and PDR001 (if applicable) and date of discontinuation for each patient.

Compliance with the protocol will be assessed by the number and proportion of patients with protocol deviations. Protocol deviations will be identified prior to database lock and will be listed and summarized.

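### SAP 2.4.2 tabulates only concomitant therapies started on or after first dose, narrower than protocol 10.3, so drugs ongoing at entry are listed but left out of the summary table

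*SAP*

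**What the plan says.** Protocol 10.3 treats listing and summary alike. Drug and non-drug co-therapy given "prior to and after the start of the study treatment will be listed by patient and summarized by ATC term and treatment group".

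SAP 2.4.2 separates the two. The listing has no restriction on start date: "Any concomitant therapies starting prior to or after the start of study treatment will be listed". The ATC and preferred-term summary is defined "to include medications or therapies starting on or after the start of study treatment but starting no later than 30 days" after the last dose. Therapies already running at first dose get their own sentence, which provides for a listing and no table: "All medications or therapies starting prior to the first dose of study treatment and continuing after the start of study treatment will be listed".

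Protocol 6.4.1 names several classes that patients may bring into the study:

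- "Anticoagulants are permitted if the patient is already at stable doses of warfarin or taking stable doses of low molecular weight heparin", the qualifying period being more than 2 weeks at the time of first dose.
- "If a patient is using an erythroid stimulating agents prior to enrollment (at least 2 weeks before start of study treatment), they may continue", with the dose unchanged.
- "Statins should be used with caution since CK elevations are commonly seen", followed by a reference to the transient CK rises seen with MCS110.

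SAP section 4 is headed as changes to protocol-specified analyses. It names 2.4.1 but not 2.4.2.

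**The concern.** A table of concomitant therapy should show what patients were taking while exposed to study drug. A rule based on start date shows only what was newly begun. Drugs carried in from before entry drop out even if they were taken throughout treatment.

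The classes affected include some that the protocol picks out for attention. Safety and tolerability are the primary objective of Phase Ib, and CK elevation is a known effect of MCS110 with its own DLT exception and dose-modification row. A reader of the clinical study report who uses the table to see how much statin use lay behind the CK findings in a group would see an under-count, and nothing in the SAP says so.

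**Working it through.** No formula or stated figure is involved, so the check compares the rules.

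**1. What each rule does with a therapy that has a complete start date**

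| Therapy | Protocol 10.3: listed | Protocol 10.3: summarised | SAP 2.4.2: listed | SAP 2.4.2: summarised |
|---|---|---|---|---|
| Stopped before first dose | yes | yes, read literally | yes, if recorded | no |
| Started before first dose, continuing on treatment | yes | yes | yes | **no** |
| Started from first dose to 30 days after last dose | yes | yes | yes | yes |

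The second row is the one that matters. The 30-day upper limit is not at fault, because protocol 7.1.5 stops collecting concomitant medication at the 30-day safety follow-up, or earlier if new antineoplastic therapy begins.

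**2. Could the SAP wording be open-ended?** The verb in the summary sentence could be read as giving examples. That is unlikely: the sentence sets both a lower and an upper limit, and a separate sentence sends therapies ongoing at first dose to a listing.

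**3. Does the SAP agree with itself?** It defines concomitant therapies by administration in the study. A drug begun earlier and taken during treatment meets that definition, yet the table of concomitant therapies leaves it out.

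**4. Which drugs fall in the second row?** Under protocol 6.4.1, an anticoagulant already at a stable dose at entry has a start date before first dose. So does an erythroid agent begun at least 2 weeks before treatment and continued. Any statin taken at entry also falls here, but the documents do not say when statins were started.

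**5. Partial start dates.** SAP 2.4.2 applies the adverse-event date rules of SAP 5.1.2. For a drug in fact begun before first dose:

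| Recorded start date | Imputed start | In the table? |
|---|---|---|
| Complete, before first dose | none needed | no |
| Month and year, same month as treatment start | treatment start + 1 | **yes** |
| Year only, same year as treatment start | treatment start + 1 | **yes** |
| Month and year, earlier month of the same year | 15th of that month | no |
| Earlier year, month missing | 1 July of that year | no |

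Two patients on the same drug for the same time can thus be treated differently because one has a less complete date.

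**6. Size per patient.** The amendment status sections give 6, 12, 12, 13, 6 and 11 patients at the Phase Ib dose levels (60 in all) and 20, 20, 21 and 20 in the Phase II groups (81 in all). One omitted user lowers the percentage in the drug row concerned by:

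- 100/6 = 16.7 points in the smallest dose level, and 100/13 = 7.7 in the largest;
- 100/20 = 5.0 points in a Phase II group of 20, and 100/21 = 4.8 in the group of 21.

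The documents give no figure for how many patients entered on such drugs, so the total shortfall cannot be computed.

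**The case against.** The best defence is that nothing is lost. Every therapy stays in a patient-level listing, and groups of 6 to 21 patients are small enough to read that way. A by-group ATC table gives marginal counts and could not in any case tie one patient's CK to that patient's statin. No analysis of CK by co-medication is planned. CK elevations are worked up patient by patient with CK-MB, troponin and muscle markers. All of this stands, and it limits the consequence to one descriptive table.

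It also disposes of several stronger readings that a reader might infer:

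- *CK and AST findings cannot be interpreted against co-medication.* The listings allow it, and protocol 6.4.1 links statins to CK only. The protocol attributes AST rises with MCS110 to reduced clearance by liver macrophages.
- *The table would show close to zero use of these classes.* Erythroid agents may be started in Phase II, after the first two cycles of dose escalation, or after a DLT, and those starts are tabulated. Some pre-entry drugs with partial dates enter too.
- *Anticoagulants are allowed only if already stable, so all users are missed.* The protocol states a condition under which they are permitted. It does not clearly bar a start on study, and protocol 6.4 generally allows medication needed for supportive care and safety.
- *Most statin use is missed.* The documents are silent on when statins were begun.
- *The silence of SAP section 4 shows a late, concealed change.* Despite its heading, that section opens as a list of updates against the first SAP. The wording of 2.4.2 may simply not have changed between versions.

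The mismatch between the two documents, and the SAP's conflict with its own definition, survive all of these points.

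**Conclusion.** The concern holds as a minor descriptive safety-reporting error. The SAP table is narrower than protocol 10.3 requires, the departure is not declared, and followed as written it under-reports co-medication during exposure by leaving out therapies already running at first dose. The date rules add some inconsistency over which of those therapies are left out.

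No efficacy endpoint, DLT count or dose decision depends on this table. The conclusion rests on reading the summary sentence of 2.4.2 as a definition, which its two limits and the separate listing sentence support. It needs no assumption about how common any drug class was at entry.

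**What to change.** Change the summary rule in SAP 2.4.2 from start date to exposure: summarise by ATC class and preferred term all concomitant therapies taken at any time from first dose to 30 days after last dose, including those started earlier and ongoing at first dose. A therapy known to be ongoing at first dose then counts whether or not its start date is complete. Showing ongoing-at-start and started-on-treatment separately is optional.

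This does not by itself meet protocol 10.3 in full, because therapies stopped before first dose would still not be summarised. Either record in SAP section 4 that those are listed only, or tabulate them separately.

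The cost is one reworded sentence in 2.4.2, one programming condition, and a line in section 4 or a further table. The records are already collected and listed, so no new data are needed.

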2.4.3 Anti-neoplastic therapies since discontinuation

Any anti-neoplastic therapies since discontinuation of study treatment will be listed.

2.5 Analysis of the primary objective

Phase Ib

The primary objective of the Phase Ib part is to characterize the safety and tolerability of MCS110 given in combination with PDR001 and to identify a recommended dose for Phase II.

Phase II

The primary objective of the Phase II part of this study is to estimate the anti-tumor activity of the combination of MCS110 with PDR001 in each expansion group.

2.5.1 Primary endpoint

2.5.1.1 Phase Ib part

The primary variables of Phase Ib are:

- Safety: Incidence and severity of AEs and SAEs, including changes in laboratory values, vital signs, and ECGs;
- Tolerability: Dose interruptions, reductions, and dose intensity;
- Incidence of DLTs in the first two cycles of study treatment.

2.5.1.2 Phase II part

For TNBC, endometrial carcinoma and melanoma the primary variable of Phase II is the Overall Response Rate (ORR), defined as the proportion of patients with a best overall response of complete response (CR) or partial response (PR) based on local Investigator assessment, as defined in RECIST v1.1. Estimation of the true ORR in this part of the study will be based upon the observed BOR for patients in the FAS, using a Bayesian analysis.

For pancreatic patients, the primary variable of Phase II is the Clinical Benefit Rate (CBR), defined as the proportion of patients with a best overall response of complete response (CR) or partial response (PR) (with at least two assessments 4 weeks apart) or stable disease (SD) > 4 months based on local Investigator assessment, as defined in RECIST v1.1. Estimation of the true CBR in this part of the study will be based upon the observed BOR for patients in the FAS, using a Bayesian analysis.

2.5.2 Statistical hypothesis, model, and method of analysis

2.5.2.1 Phase Ib part

2.5.2.1.1 Identification of a recommended dose

The dose escalation part of this study will be guided by a Bayesian analysis of first two cycles dose limiting toxicity (DLT) data for MCS110 and PDR001 in combination based on dose-determining set (DDS). If the two doses in first 2 cycles differs for one patient, the lower dose will be considered as the dose level from conservative aspect. The Bayesian analysis will be based on a model with three parts, representing:

- Single agent MCS110: $\text{logit}(\pi_1(d_1)) = \log(\alpha_1) + \beta_1 \log(d_1/d_1^*)$; $d_1^* = 5 \text{ mg/kg Q3W}$
- Single agent PDR001: $\text{logit}(\pi_2(d_2)) = \log(\alpha_2) + \beta_2 \log(d_2/d_2^*)$; $d_2^* = 300 \text{ mg Q3W}$
- Interaction: $\text{Odds}(\pi_{12}(d_1, d_2)) = \pi_{12}(d_1, d_2)/(1 - \pi_{12}(d_1, d_2))$

$$= \exp(\eta(d_1/d_1^*)(d_2/d_2^*))(\pi_1(d_1) + \pi_2(d_2) - \pi_1(d_1) \pi_2(d_2))/((1 - \pi_1(d_1))(1 - \pi_2(d_2))),$$

where $\text{logit}(\pi(d)) = \log[\pi(d)/\{1 - \pi(d)\}]$, $d_1^* = 5 \text{ mg/kg}$ and $d_2^* = 300 \text{ mg}$ are the reference doses of MCS110 and PDR001 respectively, $\alpha_1, \alpha_2, \beta_1, \beta_2 > 0$ and $-\infty < \eta < \infty$.

Single agent toxicity is modelled using logistic regression for the probability of a patient experiencing a DLT against log-dose. The odds of a DLT are then calculated under no interaction for the two single agent toxicities, and interaction is accounted for by adjusting these

odds with an additional model parameter (odds multiplier). Details of the model are given in [\[CMCS110Z2102-CSP-Section 14.4\]](#).

Assessment of patient risk

After each cohort of patients, the posterior distribution for the risk of DLT for new patients at combination doses of interest will be evaluated. The posterior distributions will be summarized to provide the posterior probability that the risk of DLT lies within the following intervals:

Under-dosing:	[0 , 0.16)
Targeted toxicity:	[0.16 , 0.33)
Excessive toxicity:	[0.33 , 1]

The escalation with overdose control (EWOC) principle

Dosing decisions are guided by the escalation with overdose control principle ([Rogatko 2007](#)). A combination dose may only be used for newly enrolled patients if the risk of excessive toxicity at that combination dose is less than 25%.

Prior distributions

For each single agent model, a mixture prior was derived. For MCS110, this study uses a mixture prior consisting of two components. Component 1 is the distribution derived based on dose-DLT data. The assigned weight for component 1 is 80%. Component 2 allows for a higher toxicity case. The assigned weight for component 2 is 20%. For PDR001, this study uses a mixture prior consisting of three components. Component 1 and 2 are derived based on dose-DLT data. The assigned total weight for component 1 and 2 is 80%. Component 3 allows for a higher toxicity case. The assigned weight for component 3 is 20%.

A meta-analytic-predictive (MAP) approach was used to derive component 1 of the prior distribution for the single agent MCS110 model parameters, and component 1 and 2 of the prior distribution for the single agent PDR001 model parameters. The MAP prior for the logistic model parameters for this study is the conditional distribution of the parameters given the historical data (see [Spiegelhalter 2004](#), [Neuenschwander 2010](#), [Neuenschwander 2014](#)). MAP priors are derived from hierarchical models, which take into account possible differences between the studies.

For this study, available clinical data were taken from the following clinical studies:

For MCS110: [\[CMCS110A2101\]](#) first-in-human MCS110 study. This study is completed. [\[CMCS110X2201\]](#) a Phase II study in PVNS patients. This study is ongoing.

For PDR001: [\[CPDR001X2101\]](#) first-in-human PDR001 oncology study. This study is ongoing.

For each of the single agent prior, an additional high toxic component is introduced to allow for a higher toxicity case. A full description of the application of the MAP approach to derive the prior distributions of the single agent MCS110 and PDR001 model parameters is given in [\[CMCS110Z2102-CSP-Section 14.4\]](#).

The prior distribution for the interaction parameter was based upon prior understanding of possible drug safety interactions (see [CMCS110Z2102-CSP-Section 1.3.3]). This prior allows for the possibility of either synergistic or antagonistic interaction, and is fully described in [CMCS110Z2102-CSP-Section 14.4].

Listing of DLTs

DLTs will be listed, and their incidence summarized by primary system organ class and preferred term and worst grade (CTCAE version 4.03). Listings and summaries will be based on the DDS.

2.5.2.1.2 Safety and tolerability analyses

See [Section 2.8](#) for details of analysis.

2.5.2.2 Phase II part

A Bayesian design will be used in order to estimate ORR (Group 1, 3 and 4) or CBR (Group 2) for each of the following groups in the Phase II part of the study.

- Group 1: MCS110 + PDR001, TNBC (naïve to PD-1/PD-L1 directed therapy)
- Group 2: MCS110 + PDR001, Pancreatic adenocarcinoma (naïve to PD-1/PD-L1 directed therapy)
- Group 3: MCS110 + PDR001, Endometrial carcinoma (naïve to PD-1/PD-L1 directed therapy)
- Group 4: MCS110 + PDR001, Melanoma (progressed on previous PD-1/PD-L1 therapy)

Each group will enroll approximately 20 patients, and may be extended to 40 patients (if at least 3 patients have an objective response for group 1, 2 and 3; and if at least 2 patients have an objective response for group 4). In addition, an exploratory group of 20 patients at a lower dose (1 mg/kg MCS110 in combination with PDR001 300 mg) may be opened if at least 3 patients have an objective response for group 2. See timing of the decision-making in [CMCS110Z2102-CSP-Section 4.2]. The primary analysis will be performed when all patients have completed at least 6 cycles of treatment or discontinued prior to that time for any reason.

Group 1, 3: Minimally informative unimodal Beta prior distribution are defined such that the prior mean ORR is set to be equal to 30% and the parameters of the minimally informative Beta prior distribution of ORR have been set up as following:

- $a/(a + b) = 0.3$
- $a = 0.43$
- $b = 1$.

At primary analysis, this prior distribution will be updated with all the data available from the patients in the FAS. Once updated, the estimate ORR and probability of ORR lies in the following categories will be reported:

- [0%, 15%] unacceptable efficacy
- [15%, 30%] moderate efficacy
- [30%, 100%] clinically relevant efficacy

If the observed ORR is equal to or greater than 30% (i.e. ≥ 12 responses (CR or PR) of out 40 patients) then this will be considered as preliminary evidence of antitumor activity of MCS110 + PDR001 in the respective patient group naive to PD-1/PD-L1 directed therapy.

Group 2: Minimally informative unimodal Beta prior distribution is defined such that the prior mean CBR is conservatively set to be equal to 15% and the parameters of the minimally informative Beta prior distribution of CBR have been set up as following:

- $a/(a + b) = 0.15$
- $a = 0.18$
- $b = 1$.

At primary analysis, this prior distribution will be updated with all the data available from the patients in the FAS. If the lower MCS110 dose level is explored (Group 2b), a separate model with the same prior assumption will be used to estimate CBR.

Once updated, the estimate CBR and probability of CBR lies in the following categories will be reported:

- [0%, 7.5%] unacceptable efficacy
- [7.5%, 15%] moderate efficacy
- [15%, 100%] clinically relevant efficacy.

Observed CBR will be analyzed by dose level. If the observed CBR is equal to or greater than 15% (i.e. ≥ 6 responses (CR, or PR, or SD for at least 4 months) out of 40 patients at RP2D; or ≥ 3 responses (CR, or PR, or SD for at least 4 months) out of 20 patients at lower dose group (Group 2b) then this will be considered as preliminary evidence of antitumor activity of MCS110 + PDR001 in the pancreatic patient group naive to PD-1/PD-L1 directed therapy.

Note that, for a sample size of $n = 40$, if the observed CBR is 15% then the posterior probability of true CBR greater than 7.5% is 93.5%; for a sample size of $n = 20$, if the observed CBR is 15% then the posterior probability of true CBR greater than 7.5% is 84.3%.

Group 4

Minimally informative unimodal Beta prior distribution are defined such that the prior mean ORR is conservatively set to be equal to 15% and the parameters of the minimally informative Beta prior distribution of ORR have been set up as following:

- $a/(a + b) = 0.15$
- $a = 0.18$
- $b = 1$.

At primary analysis, this prior distribution will be updated with all the data available from the patients in the FAS. Once updated, the estimate ORR and probability of ORR lies in the following categories will be reported:

- [0%, 7.5%] unacceptable efficacy
- [7.5%, 15%] moderate efficacy
- [15%, 100%] clinically relevant efficacy.

If the observed ORR is equal to or greater than 15% (i.e. ≥ 6 responses (CR or PR) of out 40 patients) then this will be considered as preliminary evidence of antitumor activity of MCS110 + PDR001 in the respective patient group resistant to PD-1/PD-L1 directed therapy.

2.5.3 Handling of missing values/censoring/discontinuations

Patients in the dose escalation part who are ineligible for the DDS will be excluded from the primary analysis, although their data will be used for all remaining analyses.

Patients in the phase II part who have BOR of unknown (UNK) or not assessed (NA) will be considered as a treatment failure in the primary analysis of ORR according to RECIST v1.1.

If any alternative cancer therapy is taken while on study any subsequent efficacy assessments would be excluded from all relevant efficacy summary.

Continuing events (e.g., AEs, concomitant medication, etc.) will be summarized using the data cut-off date as the date of completion, with a flag to indicate within listings that the event is continuing. For patients who discontinue the study with ongoing events, the discontinuation date will be used as the completion date of the event.

The reason for discontinuation from study will be summarized and listed.

Other missing data will simply be noted as missing on appropriate tables/listings.

